5.1.1 Methods for Generating Random Sequences

Patients who meet the inclusion criteria will be randomly assigned to either the bladder training group or the direct removal group. Stratified randomization will be performed based on the following three factors, with randomization information generated using R language on a computer. The stratification factors are: 1) Gender; 2) Whether undergoing abdominoperineal resection (APR). The randomization ratio

between the ICCAUT group and the Free-drainage group is 1:1. A random number table manager (RNTM) ([name]) from the Research Centre of Clinical Epidemiology (RCCE) at Jilin University First Hospital generates and preserves the random number table and allocates the randomization information. The RNTM is independent of other researchers in this trial.

5.1.2 Randomization concealment.

After the random number table is generated through R by RNTM, the random allocation information will be printed on paper strips and placed into opaque envelopes. The random number table and random allocation information will be kept by the RNTM from the RCCE. After clinical doctors and bedside nurses complete the patient screening and determine that a patient meets the inclusion criteria for enrollment, random allocation can be conducted. The random allocation will take place between 6:00 a.m. and 7:00 a.m. on the first day after the patient's surgery, before the intervention procedure. Clinical doctors and bedside nurses will submit an enrollment application to the RNTM and provide the patient's gender information and whether they have undergone an APR surgery. Based on the stratification corresponding to these two factors, the RNTM will deliver the opaque envelopes containing the random allocation information to the bedside nurse before 8:00 a.m. on the first day after surgery. The bedside nurse will then open the envelope and perform corresponding procedures on the patient according to the grouping information inside. The RNTM is independent of other personnel involved in this study, do not participate in any other clinical operations of this study, and have no knowledge of any other information about the patients.

5.2 Blinding and Unblinding.

This study is blinded to the physician group, the ultrasound imaging physicians who assess bladder residual urine volume, and the data analysts. The study group requires patients and assigned nurses to keep the patient's group assignment

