11.4 Efficacy analysis and statistical methods

11.4.1 Analysis of the primary endpoint

Categorical variables will be statistically analyzed and described using counts (percentages). Without performing multivariate adjustment, the primary endpoints of the two groups will be compared in the ITT analysis set, PPA analysis set, and ATA analysis set respectively. The absolute risk differences and their 95% confidence intervals (95% CI) will be used to describe the differences between the two groups. In addition, in the PPA analysis set, the chi - square test or Fisher's exact test will be used to analyze the variables related to the primary endpoint. Multivariate logistic regression will be used to adjust for factors that may affect the primary endpoint and to analyze the independent risk factors influencing the primary endpoint. During this process, continuous variables will be converted into categorical variables. The variables used for adjustment include the patient grouping (bladder training/direct removal), tumor location (the lower border of the tumor is above the peritoneal reflection/the lower border of the tumor is below the peritoneal reflection), gender (male/female), and age (≤ 65 years/ > 65 years) in the PPA dataset. Besides the above - mentioned variables, variables with a p - value < 0.1 in the univariate analysis will also be included. The adjusted differences between groups will be described using odds ratios (OR) and 95% CI.

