2.2 Treatment allocation

Patients who meet the inclusion criteria will be randomly assigned to the ICCAUT group or the free-drainage (FD) group. Stratified randomization will be performed based on the following two factors: (1) sex and (2) whether APR was performed. The allocation ratio of the ICCAUT and FD group will be 1:1.

3 Objective

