6.5 Analysis of endpoints

6.5.1 Analysis of the primary endpoint

Categorical variables will be statistically analyzed and described using counts (percentages). Without multivariate adjustment, the primary endpoints of the two groups will be compared respectively in the ITT analysis set, the PPA set, and the ATA set. The differences between the two groups will be described using the absolute risk differences (ARD) and their 95% Confidence Intervals (95% CI). The 95% CI will be compared with an absolute risk difference of 0.

The positive primary endpoint consists of bladder residual urine volume (RUV) $>100\text{ml}$ after the first voiding or secondary catheterization within 7 days after the catheter removal. These two subtypes will also be compared between the two groups and their 95% confidence interval will be presented. Also, secondary catheterization for reasons other than urinary retention will be listed in the subsets of secondary catheterization.

Primary endpoint:

Dataset: ITT, PPA and ATA				
Variables	Free-drainage group N=***	ICCAUT group N=***	Absolute risk difference (95% CI)	P value
Urinary dysfunction	** (**)	** (**)	** (** to **)	*.***
RUV >100ml	** (**)	** (**)	** (** to **)	-
Secondary catheterization	** (**)	** (**)	** (** to **)	-
Urinary retention	** (**)	** (**)	** (** to **)	-
Not urinary retention (notes on the specific reasons)	** (**)	** (**)	** (** to **)	-
Missing data	** (**)	** (**)		

In addition, in the PPA set, the Chi-square test or Fisher's exact test will be used to analyze the variables related to the primary endpoint. Multivariate logistic regression will be employed to adjust the factors that may have an impact on the primary endpoint, and to analyze the independent risk factors affecting the primary endpoint. During this process, continuous variables will be transformed into categorical variables. The variables used for adjustment include the patient grouping in the PPA dataset (ICCAUT group/free-drainage group), tumor site (the lower edge of the tumor is above the peritoneal reflection/the lower edge of the tumor is below the peritoneal reflection), sex (male/female), and age (≤ 65 years old/ > 65 years old). In addition to the above variables, variables with a p-value < 0.1 in the univariate analysis will also be included. After adjustment, the differences between the groups will be described using the Odds Ratio (OR) and 95% CI.

Univariate analysis:

Dataset: PPA	
17 Mar 2025	SAP version 1.0

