Tumor site				*.***
Above the peritoneal reflection	**(**)	**(**)		
Below or at the peritoneal reflection	**(**)	**(**)	** (** to **)	
Other variables with p value <0.1 in univariate analysis	**(**)	**(**)	** (** to **)	*.***

6.5.2 Sensitivity analysis of primary endpoints.

This study will conduct sensitivity analyses on the missing data of the primary endpoints and positive events of the primary endpoints caused by reasons other than urinary retention. The sensitivity analyses of the two situations above will be conducted in the ITT analysis set.

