6.5.2.1 Sensitivity analysis of missing data

If the missing rate of the primary endpoint is < 5%, no imputation of the primary

endpoint will be done in the ITT analysis set. If the missing rate of the final primary endpoint is $\geq 5\%$, data imputation will be carried out according to the imputation scheme for missing primary endpoint data in Figure 1 in the ITT analysis set.

For the sensitivity analysis in both of the above situations, all missing primary endpoints will be imputed as positive events or all as negative events. Then, the analysis of these two extreme cases will be performed in the ITT population.

6.5.2.2 Sensitivity analysis for positive primary endpoints caused by reasons other than urinary retention

In this study, some patients may have secondary catheterization for reasons other than urinary retention. These events can include:

- 1) Patients ask for secondary catheterization because of urgent urination or a strong fullness feeling, but the urine volume drained after secondary catheterization is no more than 100 ml.
- 2) Patients need secondary catheterization due to situations like unplanned secondary surgery, urethral injury, shock, consciousness disorder, intestinal obstruction, bleeding, transfer to ICU, etc.

In such cases, we still record it as a positive primary endpoint, but will conduct a sensitivity analysis for these cases.

For these patients:

1. If there is data on the bladder residual urine volume after the first urination and it is > 100 ml, it is still regarded as a positive primary endpoint, and no sensitivity analysis is done.
2. If there is no data on the bladder residual urine volume after the first urination or it is ≤ 100 ml, then a sensitivity analysis is needed. In the sensitivity analysis, these patients will be treated as negative events for the primary endpoint.

Sensitivity analysis of primary endpoint:

Dataset: ITT

Variables	Free-drainage group N=***	ICCAUT group N=***	Absolute risk difference (95% CI)	P value
Urinary dysfunction: all missing primary endpoints are imputed as positive events	** (**)	** (**)	** (** to **)	*.***
Urinary dysfunction: all missing primary endpoints are imputed as negative events	** (**)	** (**)	** (** to **)	*.***
Urinary dysfunction: Cases resulting from reasons other than urinary retention are defined as negative primary endpoints, and all missing primary endpoints are imputed as positive events	** (**)	** (**)	** (** to **)	*.***

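### Optional improvement: randomisation is stratified by sex and APR, but no planned ITT analysis gives a risk difference adjusted for both

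*SAP*

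**What the plan says.** **Randomisation.** SAP 2.2: "Stratified randomization will be performed based on the following two factors: (1) sex and (2) whether APR was performed". Protocol 5.1.2 (version 2.0) confirms that envelopes are issued by stratum: "Based on the stratification corresponding to these two factors, the RNTM will deliver the opaque envelopes containing the random allocation information".

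**Primary analysis.** SAP 6.5.1: "Without multivariate adjustment, the primary endpoints of the two groups will be compared respectively in the ITT analysis set". Protocol 11.4.1 says the same: "Without performing multivariate adjustment, the primary endpoints of the two groups will be compared in the ITT analysis set". The effect measure is the absolute risk difference, and its 95% CI is read against 0.

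**ITT sensitivity analyses.** The table in SAP 6.5.2 has four rows, beginning with "Urinary dysfunction: all missing primary endpoints are imputed as positive events". They vary only how missing outcomes and non-retention catheterisations are counted. None names an adjustment.

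**Adjusted model.** SAP 6.5.1: "Multivariate logistic regression will be employed to adjust the factors that may have an impact on the primary endpoint". This model is run in the per-protocol set and reports an odds ratio. Group, tumour site, sex and age are always in it. APR is one level of the surgical-procedure variable, and can enter only through the table's last line: "Other variables with p value <0.1 in univariate analysis". The anastomosis variable, a partial proxy for APR, is admitted on the same condition.

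**Subgroups.** SAP 6.5.4 plans logistic odds ratios, names no analysis set, and lists sex but not APR.

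**The concern.** A factor is usually chosen for stratification because it is expected to predict the outcome. The usual companion is an analysis that uses the strata. Here the nearest planned analysis falls short in three ways: it is per-protocol and not ITT, it gives an odds ratio and not a risk difference, and APR may drop out of it.

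What is at stake is precision. If sex and APR predict urinary dysfunction, a stratified risk difference has a smaller standard error from the same patients. If, in addition, the arms are balanced within strata, the crude confidence interval is slightly too wide, because its formula ignores the balance. The documents state no blocking, so that balance cannot be assumed.

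**Working it through.** **1. The plan's own figure.** Inputs from protocol 11.1: 44.7% vs 59.3%, 1:1 allocation, two-sided α 0.05, power 80%. With unpooled variance,

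n = (1.960 + 0.842)² × (0.447×0.553 + 0.593×0.407) / 0.146² = 7.849 × 0.4885 / 0.02132 ≈ 180 per arm.

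This matches the stated 180, and 180 / 0.9 = 200. The pooled formula gives 183. At 180 per arm the crude test has about 79–80% power, so the planned analysis delivers what was planned.

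**2. Where precision could come from.** The documents give no stratum shares and no effect of sex or APR. Assumed here: 60% men, 20% APR, additive effects, 180 per arm. Crude SE = √(0.4885/180) = 0.0521. The share of outcome variance that the strata explain is

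[gap_sex² × 0.6×0.4 + gap_APR² × 0.2×0.8] / 0.2443, where 0.2443 = 0.4885/2.

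- 10/10 points: 0.004/0.2443 = 1.6%; SE about 0.0517.
- 20/20 points: 0.016/0.2443 = 6.5%; SE about 0.0504.
- 30/20 points: 0.028/0.2443 = 11.5%; SE about 0.0490.

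Simulated mean SEs for the Mantel-Haenszel difference, balanced, were 0.0515, 0.0502 and 0.0489, against 0.0520 crude.

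**3. Power (%).** 40,000 simulated trials per setting, 360 patients; Monte Carlo SE about 0.2 point. Crude chi-square against Cochran-Mantel-Haenszel (CMH), both without continuity correction.

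| Sex/APR gap | Balanced: crude | CMH | Change | Not balanced: crude | CMH | Change |
|---|---|---|---|---|---|---|
| 0/0 | 79.9 | 79.9 | 0.0 | 79.1 | 78.5 | −0.6 |
| 10/10 | 79.9 | 80.0 | +0.1 | 79.5 | 79.5 | 0.0 |
| 20/10 | 80.3 | 81.1 | +0.8 | 79.7 | 80.9 | +1.2 |
| 20/20 | 80.6 | 82.2 | +1.6 | 79.5 | 81.7 | +2.2 |
| 30/20 | 81.2 | 84.2 | +3.0 | 79.1 | 83.3 | +4.2 |

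Repeat runs put the loss at 0/0 without balance at 0.4 to 0.5 point. With shares of 50%/10% and 70%/30% added, the change is −0.6 to 0 at 0/0, 0 to 0.1 at 10/10, 1.2 to 2.2 at 20/20 and 2.9 to 4.3 at 30/20. Using odds ratios of 1 to 4 for both factors instead of risk gaps, with balance, the gain was 0 to about 5 points.

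**4. Validity.** Crude CI coverage was 95.1–96.3% with balance and 94.8–95.0% without; Mantel-Haenszel coverage was 94.7–95.2%. Under the null at 30/20, rejection was 3.7% (crude) vs 5.0% (CMH) with balance, and 5.0% for both without.

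**5. Details the wording must settle.**

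- A continuity-corrected CMH loses 2.8 to 3.3 points against the uncorrected one. That puts it below the crude test in every balanced setting except 30/20.
- The CI with Sato variance and the CMH p-value gave different verdicts in up to 0.45% of trials.
- The smallest stratum, women with APR, has 360 × 0.4 × 0.2 / 2 ≈ 14 patients per arm under these shares, which the method handles.

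**The case against.** The strongest reply is that nothing here is wrong. The unadjusted comparison is chosen in explicit words, is the same in both documents, and reaches the planned power. Sex is handled in the per-protocol model and as a subgroup. The benefit rests entirely on assumed figures, and at modest risk gaps it disappears into simulation error. All of this stands.

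A second reply concerns timing. The SAP reports 362 of 400 enrolled. Patients are unblinded at discharge (protocol 5.2), and the DSMB discusses results with the steering committee (protocol 16). Version 2.0 has already changed the primary analysis set, the coding of events and the effect measure. Another late change to the primary estimator, for an uncertain 0 to 4 points, could cost more credibility than it buys in precision. This stands as an argument against replacing the primary estimate. It has much less force against one supportive row that leaves the primary result alone.

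A reader might go the other way and infer that ignoring the strata biases the estimate, inflates the false-positive rate or leaves the trial underpowered. The documents and the calculations support none of these. At worst the crude interval is slightly conservative, and only if the arms are balanced within strata.

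**Conclusion.** The gap is real but minor. No planned analysis gives an ITT risk difference adjusted for both randomisation factors. The crude primary analysis remains valid and unbiased and meets planned power.

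The precision forgone cannot be known from the documents. With 60% men, 20% APR, 180 per arm and additive gaps of 0/0 to 30/20 points, the power change runs from about −0.5 to +4 points. It is near zero at 10/10 and about +1.5 to +2 at 20/20. The plan lists sex among factors that may affect the endpoint, but gives no effect size for sex or APR. This is a could-do improvement.

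Protocol 5.1.1 announces "Stratified randomization will be performed based on the following three factors" and then lists two. A reader might infer that a third factor is also missing from the analysis. SAP 2.2 and the envelope procedure both work with two, so the documents do not support that. The mismatch is a separate editorial matter. So is the one-sided α in SAP 5, which would give 142 per arm (unpooled) and does not reproduce 180.

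**What to change.** Issue a dated SAP and protocol amendment before any analysis by arm, stating who has already seen endpoint data by arm. Keep the crude ITT risk difference as primary. Add one supportive ITT row to SAP 6.5.1 and protocol 11.4.1:

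*Mantel-Haenszel risk difference over the four sex × APR strata, 95% CI with Sato variance, read against 0; Cochran-Mantel-Haenszel p-value without continuity correction shown for reference.*

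Reading the CI against 0 follows the existing rule in SAP 6.5.1 and settles which of the two results decides. If multiple imputation is triggered under SAP 6.3.2, pool the Mantel-Haenszel difference and its variance by Rubin's rules. Leave the four sensitivity rows and the per-protocol and as-treated tables on the crude primary estimator.

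Make the stratified estimate primary only if the sponsor can document that no decision-maker has seen outcomes by arm. The sensitivity rows should then use the same estimator. Otherwise the change of estimator alone would shift the difference between rows: at 20/20, the 95th percentile of that shift is 0.24 point with balance and 2.8 points without.

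**Cost.** One table row and a few lines of text. No new data are needed, because both factors are given to the random number table manager at enrolment. It is a late addition to the SAP, and that row has about 0.5 point less power if the strata are not prognostic.

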6.1 General calculation rules

All statistical tests were 2-sided, and statistical significance was set at $P < 0.05$. All statistical analyses were performed using R or SPSS. P-values will be quoted to three decimal places. Confidence intervals (CI) will be two-sided and 95% CI will be quoted to one decimal place.

Categorical variables will be reported as frequencies and percentages. Percentages will be quoted to one decimal place. Chi-square tests in contingency tables will be replaced by Fisher's exact tests if any expected cell frequency is less than five. Absolute risk differences and the corresponding 95% CI will be calculated.

Continuous data with normal distribution were presented as mean (standard deviation) and analyzed by Student's t-test. Continuous variables with non-normal distribution were reported as medians (quartile) and compared using the Mann-Whitney U test. Hodges-Lehmann method will be used to calculate the difference in median and the corresponding 95% CI. Data will be quoted to one decimal place.

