6.2.2 Per-protocol analysis set

In the per-protocol analysis set (PPA), only cases that strictly follow the randomization and the assigned treatment plan will be included in the analysis. Patients who do not receive treatment according to the assigned randomization plan

will be excluded from the PPA. The excluded patients include: 1) Patients who did not have their urinary catheters removed on the second day after surgery for various reasons, with the catheter removal time being either advanced or postponed; 2) Patients who did not carry out bladder training strictly according to the plan; 3) Patients who had to use selective α 1 adrenergic receptor blockers due to their medical conditions during their first catheterization.

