Variables	Without Urinary dysfunction N=***	With Urinary dysfunction N=***	P value
Interventions			*.***
Free drainage	**(**)	**(**)	
ICCAUT	**(**)	**(**)	
Sex			*.***
Male	**(**)	**(**)	
Female	**(**)	**(**)	
Age			*.***
≤ 65 years old	**(**)	**(**)	
> 65 years old	**(**)	**(**)	
BMI			*.***
<24 kg/m^2	**(**)	**(**)	
≥24 kg/m^2	**(**)	**(**)	
ASA			*.***
I-II	**(**)	**(**)	
III-IV	**(**)	**(**)	
Neoadjuvant radiotherapy or chemoradiotherapy			*.***
No	**(**)	**(**)	
Yes	**(**)	**(**)	
Tumor site			*.***
Above the peritoneal reflection	**(**)	**(**)	
Below or at the peritoneal reflection	**(**)	**(**)	
Distance from the anal verge to the tumor			*.***
≤5 cm	**(**)	**(**)	
>5 cm	**(**)	**(**)	
Benign prostatic hyperplasia			*.***
No	**(**)	**(**)	
Yes	**(**)	**(**)	
IPSS classification at admission			*.***
Mild	**(**)	**(**)	
Moderate	**(**)	**(**)	
Severe	**(**)	**(**)	
ICIQ-SF classification at admission			*.***
No or mild	**(**)	**(**)	
Moderate	**(**)	**(**)	

Severe	**(**)	**(**)	
History of hypertension			*.***
No	**(**)	**(**)	
Yes	**(**)	**(**)	
History of Diabetes			*.***
No	**(**)	**(**)	
Yes	**(**)	**(**)	
Pathological stage T			*.***
pCR to T2	**(**)	**(**)	
T3 to T4	**(**)	**(**)	
Pathological stage N			*.***
N0	**(**)	**(**)	
N1 to N2	**(**)	**(**)	
Pathological stage TNM			*.***
0 to II	**(**)	**(**)	
III to IV	**(**)	**(**)	
Surgical techniques			*.***
Laparoscopic-assisted surgery	**(**)	**(**)	
Robotic-assisted surgery	**(**)	**(**)	
Surgical procedure			*.***
LAR	**(**)	**(**)	
APR	**(**)	**(**)	
Operation time			*.***
≤180 minutes	**(**)	**(**)	
>180 minutes	**(**)	**(**)	
Anastomosis			*.***
No anastomosis	**(**)	**(**)	
Colorectal anastomosis	**(**)	**(**)	
Coloanal anastomosis	**(**)	**(**)	
Intraoperative urine output volume			*.***
≤500 ml	**(**)	**(**)	
>500 ml	**(**)	**(**)	
Intraoperative intravenous infusion volume			*.***
≤1500 ml	**(**)	**(**)	
>1500 ml	**(**)	**(**)	
Duration of the indwelling urethral catheter			*.***

≤2 days	**(**)	**(**)	
>2 days	**(**)	**(**)	
Urinary tract infections			*.***
No	**(**)	**(**)	
Yes	**(**)	**(**)	

Multivariate analysis:

Dataset: PPA				
Variables	Without Urinary dysfunction N=***	With Urinary dysfunction N=***	Adjusted OR (95% CI)	P value
Interventions				*.***
Free drainage	**(**)	**(**)		
ICCAUT	**(**)	**(**)	** (** to **)	
Sex				*.***
Male	**(**)	**(**)	** (** to **)	
Female	**(**)	**(**)		
Age				*.***
≤ 65 years old	**(**)	**(**)		
> 65 years old	**(**)	**(**)	** (** to **)	

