6.6 Explorative analysis

We will conduct an exploratory analysis of urinary tract infections. The main focus is to explore the independent related factors affecting urinary tract infections after rectal surgery. The analysis methods include univariate analysis, multivariate analysis, and subgroup analysis.

7 Interim analyses

No interim analyses are planned in this study.

8 Timing of analysis

We will conduct the primary endpoint analysis of the study after all patients have completed their first postoperative month follow-up and will publish the relevant research findings. The results of the exploratory analysis will be published as a post hoc analysis after the publication of the primary outcomes.

9 References

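### The risk-factor search within the primary-endpoint analysis has no exploratory label or multiplicity control, and its chance findings can become extra subgroups

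*SAP*

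**What the plan says.** SAP 6.5.1 first compares the arms by an unadjusted absolute risk difference in the ITT, PPA and ATA sets. It then adds a univariate table and a multivariable logistic model in the PPA set only. The model has two jobs: to adjust for factors that may affect the endpoint, "and to analyze the independent risk factors affecting the primary endpoint". Section 11.4.1 of protocol version 2.0 gives the same second aim: "to analyze the independent risk factors influencing the primary endpoint".

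- **Entry rule.** SAP 6.5.1 says "The variables used for adjustment include the patient grouping in the PPA dataset", together with tumor site, sex and age. Beyond these, "variables with a p-value < 0.1 in the univariate analysis will also be included".
- **Size of the search.** The univariate table shell has 24 rows, each with a P value: the intervention and 23 covariates. The multivariable shell reports an adjusted OR with 95% CI and a P value for each variable in the model.
- **Threshold.** SAP 6.1 says "All statistical tests were 2-sided, and statistical significance was set at" P < 0.05. Section 6.5.1 gives no separate criterion for calling a variable a risk factor.
- **Label.** SAP 6.6 says "We will conduct an exploratory analysis of urinary tract infections", and SAP 8 and protocol 11.7 hold that work back for a separate post hoc publication. Section 6.5.1 carries no such label.
- **Later use.** Under SAP 6.5.4 and protocol 11.4.4, other variables found to be independently associated with the endpoint become further subgroups, with interaction P values.
- **A row without variation.** The PPA table includes "Duration of the indwelling urethral catheter", split at 2 days. SAP 6.2.2 removes from the PPA everyone whose catheter did not come out on postoperative day 2, "with the catheter removal time being either advanced or postponed".

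**The concern.** The plan searches a long list of covariates, selects and tests on the same data, and intends to report the survivors as independent risk factors beside the main result. The final model's P values take no account of how many candidates were searched. A similar search for urinary tract infection is called exploratory; this one is not.

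Two things are at stake. A chance association may be published as a risk factor with the standing of a primary-endpoint analysis. It may also create a data-driven subgroup in which the treatment effect is then tested for interaction.

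**Working it through.** **The plan's own figures.** The documents give no error rate for this analysis. The only design figure to reproduce is the sample size in protocol 11.1, which also supplies the event rates and the approximate number of patients used below. With rates of 44.7% and 59.3%, two-sided 0.05 and 80% power, the unpooled normal formula gives

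n = (1.96 + 0.842)² × (0.447 × 0.553 + 0.593 × 0.407) / 0.146² ≈ 180 per group.

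Then 180 / 0.90 = 200, which agrees with the plan.

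**Number of tests.** There are 24 rows. Removing the intervention leaves 23 covariates. Catheter duration has an empty upper category in the PPA, leaving 22. Sex, age and tumor site are forced into the model, so the P < 0.1 screen decides entry for the other 19 testable covariates.

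**Arithmetic for independent null covariates**, taking P < 0.05 as the implied threshold: P(at least one false factor) = 1 − 0.95^k.

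- k = 23: 0.69
- k = 22: 0.68, with 22 × 0.05 = 1.1 false factors expected
- k = 14: 0.51
- k = 10: 0.40
- k = 5: 0.23

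**Simulation of the written two-stage rule**: chi-square (or Fisher) screen at P < 0.1, treatment and the three covariates forced in, then P < 0.05 in the logistic model. The PPA size, covariate prevalences, correlations and real effects are assumptions, because the documents do not give them.

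| Setting (PPA size) | P(at least one false factor) | Mean number false |
|---|---|---|
| 23 null, independent (360) | 0.674 | 1.08 |
| 22 null, independent (360) | 0.645 | 1.04 |
| 22 null, equal latent correlation 0 / 0.2 / 0.5 (340) | 0.678 / 0.601 / 0.458 | 1.14 / 0.94 / 0.64 |
| 22 null, overlapping rows (360) | 0.567 | 0.83 |
| 22 null, overlapping rows (300) | 0.569 | 0.85 |
| Overlapping rows; sex, age and site real (360) | 0.488 | 0.68 |
| Overlapping rows; six real factors (360) | 0.611 | 0.87 |
| Overlapping rows; ten real factors (340) | 0.33 | not recorded |

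Overlapping rows means pathological T, N and TNM stage; procedure and anastomosis; tumor site and distance; sex and prostatic hyperplasia. The six-factor value exceeds the three-factor value although fewer covariates are null. One likely reason is that procedure is among the six, and the anastomosis row largely repeats it and can be counted as a false factor. Further runs varying the correlation and the number of real factors gave about 0.23 to 0.66. The lower end is what five independent null tests would give.

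**Effect of the screen.** With 23 independent null covariates, the two-stage rule gives 0.674 against 0.693 with no screen. A null covariate that reaches P < 0.05 in the model has nearly always passed P < 0.1 already, so the screen protects very little.

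**Extra subgroups.** Sex, age and tumor site are subgroups already, so only the other 19 covariates can add one. If all are null and independent, the expected number of chance-driven extra subgroups is 19 × 0.05 = 0.95.

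**The case against.** The case on the other side is substantial, and several stronger readings do not stand.

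- **A reader might infer that the SAP names a risk factor whenever P < 0.05.** It does not say so. Section 6.5.1 gives an aim, an entry rule, and ORs with CIs and P values. The threshold is inferred from SAP 6.1, the only one available.
- **A reader might divide 0.46 to 0.68 by 0.05 and report an error 9 to 14 times the stated level.** That compares a family-wide probability with a per-test level. Neither document promises a 5% family-wise rate for covariates.
- **A reader might take 0.68 as the expected figure.** It needs every covariate to be null and uncorrelated. The plan forces in sex, age and tumor site because it thinks they may matter, and several rows overlap by construction. Overlap and real factors generally lower the figure.
- **A reader might suppose that the trial's main result is at risk.** It is not. The primary comparison is the unadjusted ITT risk difference, and risk-factor identification appears in neither stated objective.
- **A formal adjustment such as Holm is not clearly required.** Practice differs for prognostic models, and covariates that fail the screen have no model P value to adjust.

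The sponsor could also point to SAP 1, which says that fixing the plan in advance helps avoid multiple-comparison problems. Prespecification limits the choice of analyses after seeing the data. It does not reduce chance findings among 22 prespecified tests. The missing label and the route into subgroups therefore remain.

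**Conclusion.** The point holds as a labelling and interpretation defect of moderate weight. Followed as written, the plan has a chance of roughly 0.2 to 0.7 of producing at least one false independent risk factor. This assumes that P < 0.05 is the naming rule and a PPA of about 300 to 360 patients. The position within the range depends on how many covariates are truly null and how strongly they overlap, neither of which the documents settle. A false factor outside sex, age and tumor site would also generate a subgroup that the plan does not name in advance.

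The catheter-duration row contradicts the PPA definition whatever view is taken of multiplicity, reading the row as the first catheterization. It cannot be tested there.

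**What to change.** - In SAP 6.5.1 and 6.5.4 and protocol 11.4.1 and 11.4.4, label the covariate screen, the covariate ORs and any subgroups derived from them as exploratory, hypothesis-generating and not adjusted for multiplicity. SAP 6.6 uses only the word exploratory, so the fuller wording would be new.
- Keep the planned ORs with 95% CIs, and state that no variable will be claimed as an independent risk factor on P < 0.05.
- Delete the catheter-duration row from the PPA univariate table.

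This changes wording and one table row. The sample size, data collection and treatment comparison stay as they are. The cost is that the report can say less about risk factors. The SAP records 362 of 400 patients enrolled when it was prepared; a label set before results are known is more credible than a caveat added afterwards.
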